5.1.2 Informed Consent

It is the responsibility of the Investigator to obtain signed written consent for the study from each patient prior to participating in the study to provide for the protection of the patients by following applicable regulations and institutional policies and procedures. The Informed Consent Form (ICF) used during the informed consent process must be reviewed by the Sponsor or designee and approved by the Institutional Review Board (IRB)/Independent Ethics Committee (IEC).

5.1.3 Medical History and Concomitant Medication Review

A detailed medical history will be obtained by the Investigator or qualified designee. This will include a comprehensive medical history and a complete review of systems, with specific attention to inclusion and exclusion criteria. The use of anti-VEGF for both eyes in the preceding 6 months prior to Screening should be documented in the concomitant medication log. All historical imaging and visual acuity assessments when available for both eyes in the preceding 6 months prior to Screening should be entered into the designated eCRF. Past medical history deemed by the Investigator as not clinically relevant to the patient's overall health status or to his or her DME will not be captured. Relevant medical history will be recorded in the electronic case report form (eCRF).

All medications taken will be recorded in the eCRF Concomitant Medication Log. Medical History and Concomitant Medication Review should log should be performed at each study visit.

5.1.4 Physical Examination

Physical examination includes assessments of the skin, head and neck, lungs, heart, abdomen, lymph nodes, extremities, and body weight. Height will be measured at Screening only.

Complete physical examinations will be performed by a licensed physician (or a physician's assistant or nurse practitioner) at Screening, Visit 9 (Week 24), Visit 12 (Week 48) or Unscheduled Visits/Early Termination (ET). After Screening, symptom-directed physical examinations are required to be performed as clinically indicated.

5.1.5 Vital Signs and Body Weight

Vital signs (blood pressure, respiratory rate, pulse rate, and oral temperature) will be obtained in the sitting position. The patient must be in the sitting position for 5 minutes prior to obtaining vital signs.

Vital signs and body weight assessment will be performed at all study visits.

5.1.6 Laboratory Tests

The Laboratory Manual contains detailed instructions for the collection and preparation of samples, directions with respect to the utilization of specialized tubes and requirements for dispensing of aliquots, and storage and shipment of samples to the Sponsor's designated central laboratory.

5.1.7 Pregnancy Test

Serum pregnancy tests will be performed at Screening, and urine pregnancy tests will be performed pre-dose on the dosing day (Day 1), Visit 9 (Week 24) and at the last study visit, Visit 12 Week 48 for all females of childbearing potential.

5.1.8 Electrocardiography

Evaluation will be performed at Screening for baseline reference, Visit 9 (Week 24) and at the last study visit, Visit 12 (Week 48).

5.1.9 Ocular Evaluations (must be conducted on both eyes)

- BCVA: should be assessed using the ETDRS chart starting at 4 meters at Screening, on Day 1 (pre-dose), Day 2, and at Weeks 1, 2, 4, 8, 12, 18, 24, 32 and 48, and Unscheduled/ET. See the Ophthalmic Manual for details.
- Anterior Segment Evaluation: should be performed prior to pupillary dilation, or after, depending on the site Standard of Care. Any abnormalities of the anterior chamber, eyelids, conjunctivae, pupil, iris, lens and cornea should be documented at Screening, on Day 1 pre-dose and post-dose, on Day 2, and at Weeks 1, 2, 4, 8, 12, 24, 32 and 48 and Unscheduled/ET. Any anterior chamber inflammation (cells and flare), phakic status, and posterior lens capsule status should also be noted. For post-dose, only the study eye should be assessed
- Posterior Segment Evaluation/Ophthalmoscope Examination: should be performed after pupillary dilation to examine the vitreous body, optic nerve head, macula, posterior pole, and peripheral retina at Screening, on Day 1 pre-dose and post-dose, on Day 2, and at

Weeks 1, 2, 4, 8, 12, 24, 32 and 48/ET. Any vitreous inflammation (haze and cells) should also be noted. For post-dose, only the study eye should be assessed

- IOP: should be measured using Goldmann applanation tonometry at Screening, on Day 1 pre-dose and 30 minutes ± 15 minutes post-dose, on Day 2, and at Weeks 1, 2, 4, 8, 12, 24, 32 and 48 and Unscheduled/ET. Tonometry should be performed prior to pupillary dilation or as per site's standard procedures. For post-dose, only the study eye should be assessed
- CFP: should be obtained at Screening, Visit 9 (Week 24), Visit 12 (Week 48) and Unscheduled/ET.
- FA: should be obtained at Screening (or on Day 1 pre-dose) and at Weeks 4, 12, 24 and 48, and Unscheduled/ET (if it had not been done within 30 days prior).
- SD-OCT: should be obtained at Screening, on Day 1 (pre-dose), and at Weeks 1, 2, 4,8, 12, 18, 24, 32, 40 and 48 and Unscheduled/ET.
- OCT-A: to be conducted at sites with the proper equipment available at Screening, Weeks 12, 24 and 48 and Unscheduled/ET.

CFP, FA, SD-OCT, and OCT-A (if done) images should be transmitted to the Central Reading Center at each applicable visit.

5.1.10 Rescue Criteria

If at any visit between Visit 4 (Week 2) to Visit 12 (Week 48) or Unscheduled, patients exhibit worsening CST by 75 µm from Baseline (Day 1) per SD-OCT and/or a 10-letter decrease in BCVA compared to peak BCVA from Baseline (Day 1), they can be rescued with standard of care. For this study, standard of care is defined as the last anti-VEGF a patient was administered prior to enrolling into the study. Rescued patients will continue their visit schedule as safety follow-up through Week 48. For any questions on rescue criteria, and prior to administering rescue medication, when possible, please contact the Medical Monitor or designee. Rescued patients continue with study visits per protocol. If additional visits are required outside of study visit windows, these will be considered unscheduled visits.

5.1.11 End of Study

The study will be considered complete when the last patient has completed the last study visit.

5.2 Discontinuation or Withdrawal

5.2.1 Individual Patients

5.2.1.1 Withdrawal from Study

Patients can voluntarily withdraw from the study for any reason at any time. They are to be considered withdrawn if they state an intention to withdraw, fail to return for visits, or become lost to follow-up for any reason. Patients withdrawing from the study because of an AE should be followed for at least 30 days, until resolution of the AE, or until no further improvement is expected, whichever comes first. Patients withdrawing from the study should be encouraged tocomplete all assessments under the Unscheduled/ET visit described in Table 1.

The Investigator may withdraw a patient from the study for any of the following reasons:

- A protocol violation occurs,
- Lack of efficacy,
- A serious or intolerable AE occurs,
- The Sponsor terminates the study,
- The Investigator suspends or terminates that site's participation in the study, or
- The patient requests to be discontinued from the study.

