7.2 Documenting Adverse Events

7.2.1 Timeframe for Collection

AEs and SAEs will be collected from the time of treatment through the last follow-up visit at Week 48. All events prior to this will be documented as medical history.

The Investigator must follow up on all AEs through Week 48. Non-serious AEs may be followed to resolution past the patient's last study visit at the discretion of the Investigator and/or MedicalMonitor if in the best interest of the patient and the assessment of safety of UBX1325. The Investigator must follow up on all SAEs until the events have subsided, returned to Baseline, or,in case of permanent impairment, the condition stabilizes.

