1.3 Study endpoints

1.3.1 Primary endpoint

• Ocular and systemic safety and tolerability of a single IVT injection of UBX1325 evaluated by treatment emergent adverse events (TEAEs)

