12.1 Appendix A – Schedule of Events (Protocol Table 1)

Table 1 Schedule of Events

	Screening Dav -42 to	Visit 1 Week 0	Visit 2 24 ± 4 hours Observation ^a	Visit 3 Week 1 Dav 8	Visit 4 Week 2 Dav 15	Visit 5 Week 4 Day 29	Visit 6 Week 8 Dav 57	Visit 7 Week 12 Day 85	Visit 8 Week 18 Dav 127	Visit 9 Week 24 Dav 169
Test/Procedure	Day -1	Day 1	Day 2	∓ I	±2	±1	±7	1 +	±1	±7
Informed Consent	X									
Demographics	X									
Medical/ Onhthalmic	A	A	Λ	X	A	A	Λ	X	X	A
History	<	4	<	4	<	<	<	v	¢	¢
Medication History/	P	1	2	1	Ŷ	2	1			
Concomitant Medications	×	v	V	V	×	v	v	V	v	V
Physical Examination	x									x
Vital Signs and Weight	x ^b	х	Х	х	Х	х	Х	х	х	х
Laboratory Tests: Hematology and Chemistry	х	-								х
Pregnancy Test	X (serum)	X (urine) ^c								X (urine) ^c
12-Lead ECG	X									X
BCVA	Х	Х	Х	Х	Х	Х	Х	X	X	Х
Anterior Segment Evaluation	Х	рX	Х	Х	X	Х	Х	Х		Х
Posterior	Λ	pA	Λ	X	Λ	A	X	A		Λ
Evaluation	¢	-V	v	4	4	4	4	v		V
IOP	Х	рX	Х	Х	Х	Х	Х	X		Х
SD-OCT ^e	Х	Х		Х	Х	Х	Х	X	Х	Х
OCT-A ^e	х							X		Х
FAe	X					Х		X		X

echnology	UBX1325-02
Unity Biot	Protocol:

Statistical Analysis Plan Version 1.0

			Visit 2	Visit 3	Visit 4	Visit 5	Visit 6	Visit 7	Visit 8	Visit 9
	Screening	Visit 1	24 ± 4 hours	Week 1	Week 2	Week 4	Week 8	Week 12	Week 18	Week 24
	Day -42 to	Week 0	Observation ^a	Day 8	Day 15	Day 29	Day 57	Day 85	Day 127	Day 169
Test/Procedure	Day -1	Day 1	Day 2	±1	±2	±7	±7	±7	±7	±7
CFPe	Х							Х		Х
DRSS score	Х							Х		Х
Eligibility Criteria	Х	X								
Study Drug Administration ^g		Х								
AE assessment		X	X	X	Х	Х	X	X	Х	Х

Schedule of Events (Continued) Table 1

cedure	Visit 10 Week 32 Day 225 ± 7	Visit 11 Week 40 Day 281 ± 7	Visit 12 Week 48 Day 337 ± 7	Unscheduled Visit/ET
thalmic	X	x	X	х
comitant	Х	Х	Х	Х
amination			X	X
and Weight	X	X	X	X
Tests: y and			Х	Х
Test			X (urine)	
G			X	X
	Х	X	Х	Х
gment	Х	Х	Х	Х
egment	Х	Х	Х	Х
	X	X	X	X
	X	X	X	X
			X	X
			Х	X^{f}
			Х	Х
0			Х	Х
nent	X	X	X	X

ALL - adverse event, DC VA - Dest corrected visual adury; CFF - color tunuus photography; DFG > - datrete reunopanty seventy scores; ECG = electrocardiogram; ET = early termination; FA = fluorescein angiography; IOP = intraocular pressure; OCT-A = optical coherence tomography angiography; SD-OCT = spectral domain optical coherence tomography; rescue treatment administered if needed Procedures to be performed at the end of the ~ 24 hours) of observation.

- ^b Height should also be measured at Screening.

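### The follow-up rule for patients who withdraw because of an AE contradicts itself and does not agree with the general AE and SAE follow-up rule

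*Protocol*

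**What the plan says.** Protocol 5.2.1.1 (Withdrawal from Study) states of patients whose withdrawal is due to an AE that they "should be followed for at least 30 days, until resolution of the AE, or until no further improvement is expected, whichever comes first". The same section lists the reasons for which the Investigator may withdraw a patient, and one of them is "A serious or intolerable AE occurs". The follow-up sentence makes no exception for serious events and does not say from which day the 30 days run.

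Protocol 7.2.1 (Timeframe for Collection) sets the general rule. On collection: "AEs and SAEs will be collected from the time of treatment through the last follow-up visit at Week 48". On follow-up of AEs: "The Investigator must follow up on all AEs through Week 48". On serious events: "The Investigator must follow up on all SAEs until the events have subsided, returned to Baseline", or, where impairment is permanent, until the condition is stable. It makes no exception for withdrawn patients.

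Neither section refers to the other. SAP 3.5 provides only for data collection at the Early Termination visit, so the SAP does not settle the matter.

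**The concern.** A site with a patient who has just withdrawn because of an AE has two instructions on when follow-up may stop, and the first does not agree with itself. The two instructions can apply to the same event, including an SAE.

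These are the patients whose event was bad enough to end participation. The main stake is their safety follow-up. A second stake is the data. The primary endpoint is safety assessed by TEAEs, and SAP 8.1 tabulates worst severity, grade 3 or higher, serious and fatal events. If follow-up stops early, a later worsening of the event that led to withdrawal may not be recorded.

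**Working it through.** The documents give no figure to reproduce. The check compares the wording and then works out the days involved.

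**Step 1: the sentence in 5.2.1.1 against itself.** The word 'least' makes 30 days a floor. The closing clause makes the earliest of three limbs the end, so 30 days becomes a ceiling. Two cases show the clash:

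- The AE resolves 5 days after withdrawal. The floor requires 30 − 5 = 25 more days; the earliest-of clause ends follow-up at once.
- The AE is unresolved at 30 days. The floor allows follow-up to continue; the earliest-of clause ends it.

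A site could rescue the sentence by taking 30 days as a floor and applying the earliest-of clause only to the other two limbs. The punctuation does not signal that reading, and nothing else in the protocol selects it.

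**Step 2: 5.2.1.1 against 7.2.1.**

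| Event in a patient who withdrew because of it | 5.2.1.1, literal reading | 7.2.1 |
|---|---|---|
| Non-serious AE, unresolved at 30 days | may stop | follow through Week 48 |
| SAE, unresolved and not stable at 30 days | may stop | continue until subsided, back to Baseline or stable |
| SAE that has resolved | may stop | may stop |

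The resolution limb broadly agrees with the SAE rule, so the SAE conflict comes mainly from the 30-day limb. The limb about no further improvement can also differ from stability, because an event may have no prospect of improving and still be getting worse.

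**Step 3: days involved.** Week 48 is given in the schedule of events (SAP Appendix A) as "Visit 12 Week 48 Day 337 ± 7". Assume that the 30 days run from the day of withdrawal, W. Then:

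- literal end of follow-up = W + 30
- shortfall against Week 48 = 337 − (W + 30) = 307 − W

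| Withdrawal | W | W + 30 | Shortfall (days) |
|---|---|---|---|
| Week 1 | 8 | 38 | 299 |
| Week 4 | 29 | 59 | 278 |
| Week 12 | 85 | 115 | 222 |
| Week 24 | 169 | 199 | 138 |

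The 30-day limb falls short of Week 48 for any withdrawal before Day 307. With the ±7-day visit window this becomes Day 300 to Day 314.

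**Step 4: number of patients.** The sample-size section (Protocol 8.2, SAP 2.4) assumes 5% drop-out: 62 × 0.05 = 3.1, about 3 patients from all causes. Those who withdraw because of an AE that is still unresolved at 30 days are a subset, for which the documents give no rate.

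**The case against.** The strongest reply is that both rules can be obeyed together. Section 5.2.1.1 says what should be done and sets a minimum; 7.2.1 says what the Investigator must do, for all AEs and all SAEs. A site that follows 7.2.1 does not breach the minimum. This is a sensible way to act, but it ignores the earliest-of clause, and a site that reads only the withdrawal section is told something else.

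A second reply is that 5.2.1.1 is the specific rule for withdrawals, since 7.2.1 ties collection to a Week 48 visit that a withdrawn patient does not attend. That is plausible, but the protocol does not say so, and the clash within the sentence would remain. It is also true that patients lost to follow-up cannot be followed under either rule. Section 5.2.1.1 nevertheless asks for follow-up after an AE withdrawal.

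A third reply is that Protocol 7.3 requires immediate reporting of related SAEs that come to light outside the reporting period. It is only a partial backstop, because it covers only SAEs judged possibly or probably related.

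The reply on the primary endpoint largely stands. The AE that led to withdrawal has already occurred and been recorded, and its resolution date and outcome enter none of the summaries listed in SAP 8.1. Only later worsening in severity, seriousness or death could change a table.

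**Conclusion.** The inconsistency is real, both within 5.2.1.1 and between it and 7.2.1. It bears on patient safety follow-up, and in a limited way on capture of later worsening. Severity is minor: at most about 3 of 62 patients on the plan's own all-cause drop-out assumption, and probably fewer.

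Three stronger inferences are not supported:

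- *These patients are lost from the primary analysis.* They are not. Every treated patient stays in the Safety Analysis Set (SAP Section 4), and the event that led to withdrawal is counted.
- *Follow-up will typically differ by about 300 days between sites.* The 299 days is close to the worst case. It needs withdrawal at Week 1, an event that never resolves, a site that treats the minimum as a cap and sets 7.2.1 aside, and a 30-day clock that starts at withdrawal.
- *The SAP lacks a listing of outcome or last contact for these events.* This cannot be shown. SAP 8.1 already lists all AEs in the clinical database, and SAP Section 1 places the table and listing specifications in a separate document.

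The conclusion on wording rests on no assumption. The day counts rest on the assumed start point, and the patient count on the assumed 5%.

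**What to change.** Reconcile Protocol 5.2.1.1 with 7.2.1 so that one rule defines when AE and SAE follow-up ends after withdrawal. In doing so:

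- remove the clash between the minimum duration and the earliest-of clause;
- state the day from which any fixed period runs;
- say whether the rule for SAEs differs from that for other AEs;
- cross-reference the two sections.

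Which end point applies is a clinical decision for the sponsor's medical team, and no view on it is given here. The cost is about one sentence plus the cross-references, in a protocol amendment or clarification letter. No change to the SAP is needed on this point.

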6.8.2 Prohibited Treatments

Patients will not be permitted to received treatments for the management of DME in the study eye, once randomized to this study, unless it is a rescue treatment (see Section 5.1.11).

Systemic (oral, intramuscular, and intravenous) steroids are not allowed unless for an AE treatment. All systemic steroids should be discontinued before the study drug administration.

Patients should not have received any therapy that would preclude an IVT injection or can potentially exhibit retinal toxicity (such as tamoxifen, hydroxychloroquine and trastuzumab).

Patients are prohibited from receiving any medication for the study eye that, in the opinion of the Investigator and/or the Medical Monitor, may have an effect on the study results.

Patients should not have received brolucizumab as their most recent anti-VEGF treatment. Historical use of brolucizumab is not excluded.

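### After a single Day 1 dose, Protocol 5.2.1.1 lets the investigator end follow-up for lack of efficacy or a protocol violation: an avoidable, probably small loss of late data

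*Protocol*

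**What the plan says.** Protocol 5.2.1.1 (Withdrawal from Study) states: "The Investigator may withdraw a patient from the study for any of the following reasons". Two of the listed reasons are "A protocol violation occurs" and "Lack of efficacy". Neither has a definition or threshold, and both concern the study, not only treatment. Afterwards the section offers one early-termination (ET) visit, and even that is soft: "Patients withdrawing from the study should be encouraged" to complete it.

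Other parts of the plan point the other way:

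- The Synopsis and Protocol 4.1 give one administration on Day 1 and about 48 weeks of follow-up for every patient.
- Protocol 5.1.10 says of patients who worsen past a threshold (CST up 75 µm and/or a 10-letter loss from peak) that "they can be rescued with standard of care". It keeps them on the visit schedule through Week 48, and SAP 7.1 repeats that they continue.
- Protocol 6.7 asks accidentally unmasked patients to continue through Week 48 (SAP 2.3 says Week 24).
- Protocol 10.2.2 deals with deviations by documentation and reporting. It does not call for withdrawal.
- Protocol 6.8.2 bars "treatments for the management of DME in the study eye, once randomized to this study, unless it is a rescue treatment".

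**The concern.** In a trial with repeated dosing, an investigator may stop treatment because it is not working, and that limits exposure. Here nothing is left to stop after Day 1. Withdrawal for lack of efficacy or for a violation ends scheduled observation and, with it, the ban on non-rescue DME treatment. It protects the patient from no further study drug.

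The two reasons differ in kind. Lack-of-efficacy withdrawal depends on outcome and, if the drug works, would be expected more often on sham. Violation withdrawal is not inherently related to outcome, but it is loss without a purpose.

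Both rescue and withdrawal are discretionary. One site may rescue and keep a worsening patient while another withdraws a similar one. Four results are exposed:

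- detection of new late treatment-emergent adverse events, which are the primary endpoint, collected to Week 48;
- the supportive BCVA analysis of all data regardless of rescue;
- macular-fluid status at Weeks 24 and 48;
- the proportions needing rescue by Weeks 24 and 48.

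Protocol 8.1 imputes nothing, and SAP 7.1 gives no denominator rule for early leavers from the binary endpoints.

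**Working it through.** **Sample size (Protocol 8.2; SAP 2.4).** Inputs: difference 8 letters, SD 13, two-sided alpha 0.15, power 80%, drop-out 5%.

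- Normal approximation: 2 × (1.440 + 0.842)² × (13/8)² = 27.5, so 28 per arm; 28/0.95 = 29.5, so 30 per arm.
- Two-sample t: 29 per arm; 29/0.95 = 30.5, so 31 per arm and 62 in total. This reproduces the plan's figure.
- Power with 31 randomized per arm (normal / t): 82.2% / 81.6% at 5% loss and 80.5% / 79.9% at an assumed 10% loss. The sample size is not in question.

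**Size of the allowance.** 0.05 × 62 = 3.1, so about 3 patients for all reasons in both arms. The documents give no expected number of withdrawals for the two reasons at issue.

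**Visits lost (Protocol Table 1).** Eleven visits follow Day 1 (Visits 2 to 12). After withdrawal at Week 12 (Day 85), those on Days 127, 169, 225, 281 and 337 are lost: 5 of 11. Scheduled observation lost: (337 − 85)/(337 − 1) = 252/336 = 75%.

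**Macular fluid (SAP Table B.1).** The windows are Days 148–196 for Week 24 and Days 309–519 for Week 48. Assume withdrawal between Day 15 (Week 2, the first rescue visit) and Day 336, with the ET visit done the same day. That range has 322 days.

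- Week 48 status is lost for Days 15–308: 294/322 = 91%.
- Week 24 status is lost as well for Days 15–147: 133/322 = 41%.

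These are shares of calendar days, not probabilities. The timing of withdrawal is unknown.

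**Rescue proportion, per sham patient withdrawn before an event that would have counted (31 per arm).**

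- Kept as a non-event: 1/31 = 3.2 points off the sham-minus-active difference, whatever the true rate.
- Dropped from the denominator, at assumed true sham rates of 8/31, 15/31 and 22/31: 7/30 − 8/31 = −2.5; 14/30 − 15/31 = −1.7; 21/30 − 22/31 = −1.0 points.
- Extreme case, with all 3 patients of the allowance being such sham patients: 3/31 = 9.7 points as non-events. If dropped: 5/28 − 8/31 = −7.9; 12/28 − 15/31 = −5.5; 19/28 − 22/31 = −3.1 points.
- Milder case, 2 sham and 1 active lost, assumed truth 15/31 v 9/31 (difference 6/31 = 19.4 points): 13/31 − 8/31 = 16.1 if non-events; 13/29 − 8/30 = 18.2 if dropped.
- For scale, the score 95% interval for 15/31 v 9/31 is −5.1 to 41.2, a half-width of about 23 points. The SAP's exact interval was not reproduced. Every shift above is smaller than this half-width.

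**The case against.** **The exposure to bias is limited.** The rule is permissive and investigators are masked. The main route for a failing patient is rescue, which keeps follow-up. The primary BCVA analysis stops at rescue in any case and uses every visit before dropout. A likelihood-based MMRM is valid if withdrawal depends on BCVA already recorded, and a masked investigator acting on recorded letters is close to that. Known adverse events must be followed through Week 48 (Protocol 7.2.1). Possibly or probably related serious events that come to the investigator's attention outside the reporting period must still be reported (Protocol 7.3). Major eligibility violators are already excluded from the BCVA models, so keeping them helps only the safety and binary endpoints. All of this stands, and it is why the point is minor.

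**Stronger readings that a reader might infer.**

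- *The BCVA comparison is biased or underpowered.* The documents do not support this. A completers-only calculation that removes the lowest 10% of sham and 5% of active outcomes would shrink a true 8-letter difference to 6.9 letters. The plan does not analyse completers only, and those rates are assumed.
- *The plan forces patients to leave to get other care, so the ban in 6.8.2 needs an exception.* Rescue does need threshold worsening, and "standard of care is defined as the last anti-VEGF a patient was administered prior to enrolling into the study", so a patient with persistent edema below the threshold has no on-protocol route to treatment. But withdrawal is optional, and treatment outside the rule is a deviation that 10.2.2 handles without ending follow-up. Entry requires CST of at least 300 µm (Protocol 4.5), so edema is present from the start. A discretionary exception for sub-threshold edema could undo the objective rescue threshold and contaminate the macular-fluid results. Through steroid use it could also affect IOP and ocular adverse events. It would not restore the rescue counts either, because non-rescue treatment may prevent the counted event.
- *Missing a visit bars a patient for good.* Protocol 5.2.1.1 counts as withdrawn those who "fail to return for visits, or become lost to follow-up for any reason", but no text prevents their return. This is missing detail, not a further fault.

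**Conclusion.** The point holds as a cheap improvement of minor severity. Two of the listed reasons for study withdrawal have no exposure-limiting purpose after a single Day 1 dose and sit badly with a plan that keeps rescued and unmasked patients in follow-up. One of the two is outcome-related and could differ by arm.

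The effect is probably small: at most 3.2 points per lost sham rescue event, and 9.7 points if the entire drop-out allowance were such patients. For an individual, withdrawal at Week 12 removes three quarters of scheduled observation for new events. These figures rest on 31 patients per arm, assumed event rates, and an ET visit that actually takes place. How often investigators would use the rule cannot be learned from the documents. The primary BCVA model would gain little from the change; the gain is in late safety detection, the supportive analysis and the late binary endpoints.

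**What to change.** **Protocol 5.2.1.1.** Delete the protocol-violation and lack-of-efficacy reasons. State that such patients continue visits to Week 48 unless they withdraw consent, and that patients who worsen are managed under 5.1.10. Add that any DME treatment given in the study eye outside 5.1.10 is recorded with its date as a deviation under 10.2.2 and does not end follow-up. Leave the adverse-event, sponsor, site and patient-request reasons unchanged.

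**SAP 7.1.** Cut the primary BCVA and CST analyses at the first such treatment, as for rescue, and keep later data in the supportive analysis. Report the number of patients so treated, by arm, beside the rescue and macular-fluid proportions.

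**What not to change.** Do not add a general exception to 6.8.2, and do not permit treatment of sub-threshold edema at investigator discretion.

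**Cost.** A few sentences in each document and a few more visits that are already scheduled. The sample size does not change. Some late macular-fluid and supportive data will reflect off-protocol treatment, and a rescue event prevented by such treatment will still go uncounted. The by-arm count makes this visible but does not remove it.
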